#### 10.2.4. Recording and Follow-Up of AE/TEAE and/or SAE/TESAE

AE and SAE Recording

 
• When an AE/TEAE or SAE/TESAE occurs, it is the responsibility of the Investigator to review all documentation (e.g., hospital progress notes, laboratory reports, and diagnostics reports) related to the event.
 
• The Investigator will then record all relevant AE/TEAE and SAE/TESAE information in the CRF.
 
• It is not acceptable for the Investigator to send photocopies of the Participant’s medical records to the Sponsor or designee in lieu of completion of the AE/SAE CRF page.
 
• Instances may arise when copies of medical records for certain cases are requested by the Sponsor or designee. In this case, all Participant identifiers, with the exception of the Participant number, will be redacted on the copies of the medical records before submission to the Sponsor or designee.
 
• The Investigator will attempt to establish a diagnosis of the event based on signs, symptoms, and/or other clinical information. Whenever possible, the diagnosis (not the individual signs/symptoms) will be documented as the AE/SAE.
 

### Assessment of Intensity

The Investigator will make an assessment of intensity for each AE and SAE reported during the study and assign it to 1 of the following categories:

- Mild: An event that is easily tolerated by the Participant, causing minimal discomfort and not interfering with everyday activities.
- Moderate: An event that causes sufficient discomfort and interferes with normal everyday activities.
- Severe: An event that prevents normal everyday activities. An AE that is assessed as severe should not be confused with an SAE. Severe is a category used for rating the intensity of an event; and both AEs and SAEs can be assessed as severe.

An event is defined as “serious” when it meets at least 1 of the predefined outcomes as described in the definition of an SAE, NOT when it is rated as severe.

### Assessment of Causality

- The Investigator is obligated to assess the relationship between study intervention and each occurrence of each AE/SAE.
- A “reasonable possibility” of a relationship conveys that there are facts, evidence, and/or arguments to suggest a causal relationship, rather than that a relationship cannot be ruled out.
- The Investigator will use clinical judgment to determine the relationship.
- Alternative causes, such as underlying disease(s), concomitant therapy, and other risk factors, as well as the temporal relationship of the event to study intervention administration will be considered and investigated.
- The Investigator will also consult the IB and/or Product Information, for marketed products, in his/her assessment.
- For each AE/SAE, the Investigator **must** document in the medical notes that he/she has reviewed the AE/SAE and has provided an assessment of causality.
- Situations may arise in which an SAE has occurred, and the Investigator has minimal information to include in the initial report to the Sponsor or designee. However, the Investigator must always assess causality for every event before the initial transmission of the SAE data to the Sponsor or designee. Death or hospitalization are not to be specified as an SAE; these are criteria to determine seriousness.
- The Investigator may change his/her opinion of causality in light of follow-up information and send an SAE follow-up report with the updated causality assessment.
- The causality assessment is one of the criteria used when determining regulatory reporting requirements.

**Follow-up of AEs and SAEs**

- The Investigator is obligated to perform or arrange for the conduct of supplemental measurements and/or evaluations as medically indicated or as requested by the Sponsor or designee to elucidate the nature and/or causality of the AE or SAE as fully as possible. This may include additional laboratory tests or investigations, histopathological examinations, or consultation with other health care professionals. New or updated information will be recorded in the originally completed CRF.
- The Investigator will submit any updated SAE data to the Sponsor or designee within 24 hours of receipt of the information.

**10.2.5. Reporting of SAEs/TEAEs****SAE Reporting to the Sponsor or Designee via an Electronic Data Collection Tool**

- The primary mechanism for reporting an SAE to the Sponsor or designee will be the electronic data collection tool.
- The Site will enter the SAE data into the electronic system as soon as it becomes available.
- After the study is completed at a given Site, the electronic data collection tool will be taken off-line to prevent the entry of new data or changes to existing data.
- If a Site receives a report of a new SAE from a study Participant or receives updated data on a previously reported SAE after the electronic data collection tool has been taken off-line, then the Site can report this information or to the Medical Monitor or SAE coordinator by telephone.

### 10.3. Appendix 3. Grading of Injection Site Reactions

A global assessment across all injection sites on each leg is to be performed following each treatment. The injection site reaction with the most severe pain/tenderness, erythema/itching/urticaria, and bruising/swelling/bleeding on each leg is to be used for reporting injection site reaction grades (mild, moderate, severe, or life-threatening) following each treatment. Severe (Grade 3) and potentially life-threatening (Grade 4) Injection Site Reactions will be AESIs. Two sources were used for compiling the following grading guidelines for Injection Site Reactions (Table 6):

1. FDA Guidance: Toxicity Grading Scale for Healthy Adult and Adolescent Volunteers Enrolled in Preventive Vaccine Clinical Trials, September 2007.
2. National Cancer Institute: Common Terminology Criteria for Adverse Events (CTCAE) v5.0, Nov. 27, 2017.

**Table 6 Injection Site Reaction Grading**

Reaction at Injection Site a	Mild (Grade 1)	Moderate (Grade 2)	Severe (Grade 3)	Potentially Life-Threatening (Grade 4)
Pain, tenderness	Mild discomfort to touch, with or without warmth, erythema, itching  Does not interfere with daily activity  No or local treatment	Symptoms with or without swelling and/or phlebitis  Interferes with daily activity  Use of non-narcotic pain reliever	Symptoms with or without swelling or phlebitis or mild infection  Precludes daily activity  Use of narcotic pain reliever and/or oral antibiotics	Symptoms with severe infection or tissue injury or ulceration  Requires advanced medical and/or surgical care, including IV medications
Erythema, itching, urticaria	Mild, localized itching, erythema or urticaria.  Does not interfere with activity  Use of topical treatment	Symptoms with skin changes beyond local injection site(s)  Interferes with movement and daily activity  Use of NSAIDs and/or antihistamines	Symptoms with widespread skin changes  Interferes with daily activity  Use of oral steroids or immunosuppressives	Bronchospasm, anaphylactoid, or anaphylactic reaction  Requires advanced medical care, including IV medication
Bruising, swelling, bleeding	Mild, localized swelling, ecchymosis or hematoma  Does not interfere with activity  No treatment	Moderate ecchymosis or hematoma  Interferes with daily activity  Requires leg elevation, conservative treatment	Extensive ecchymoses, large hematoma  Precludes activity  Requires minimally invasive drainage	Hypotension, life-threatening consequences  Requires transfusion, urgent intervention

a Injection Site Reactions are a category of AEs and should be recorded as AEs using these grading guidelines.

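### Table 6: function does not rise from Grade 2 to Grade 3 in the erythema/itching/urticaria row, so erythema that prevents daily activity but is not widespread stays below the AESI threshold

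*Protocol*

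**What the plan says.** Protocol Section 10.3 asks for a global assessment of all injection sites on each leg after each treatment, graded on a four-level scale in Table 6. The table has three rows: pain/tenderness, erythema/itching/urticaria, and bruising/swelling/bleeding. Most cells combine a description of the reaction, a functional line and a treatment line.

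In the erythema row:
- Grade 2: skin changes reach past the local injection sites; function is "Interferes with movement and daily activity"; treatment is NSAIDs and/or antihistamines.
- Grade 3: "Symptoms with widespread skin changes"; function is interference with daily activity, with movement no longer mentioned; treatment is "Use of oral steroids or immunosuppressives".

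In the pain row, the Grade 3 functional line is "Precludes daily activity".

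Sections 8.5.4.3 and 10.3 make Grade 3 or 4 in Table 6 the condition for an injection site reaction to count as an AESI. Section 6.7.1 and Table 7 rule out oral corticosteroids during the study, with a maximum allowed dose of none and no exception for treating a reaction.

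**The concern.** The Grade 2/3 boundary is the AESI threshold, so each row should separate the two grades on every dimension it uses. In the erythema row the functional line does not. Read literally, Grade 3 asks for slightly less than Grade 2, because movement drops out. A participant whose itching or urticaria prevents normal activity, but whose skin changes are not widespread, fits no Grade 3 description in that row.

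At stake is the grade recorded for such a reaction and whether it is flagged as an AESI. The grade feeds the SAP 8.5.2 summary of injection site events by grade and the injection site reaction severity shown under AESI in SAP 8.5.3. AESIs are also among the data that the DSMB reviews (Protocol Section 10.1.5.1).

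**Working it through.** The plan states no figure for this point, so the check is a comparison of cells.

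**Step 1. Functional line by row (Table 6).**

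| Row | Grade 2 | Grade 3 | Step up? |
|---|---|---|---|
| Pain, tenderness | interferes | precludes | yes |
| Erythema, itching, urticaria | interferes (movement and daily activity) | interferes (daily activity only) | no |
| Bruising, swelling, bleeding | interferes | precludes | yes |

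Two of three rows have the step. The erythema row is the only one without it.

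**Step 2. What else separates Grade 2 from Grade 3 in the erythema row.**
- Extent: beyond the local sites against widespread. The order is clear, but neither term has a measure.
- Treatment: NSAIDs or antihistamines against oral steroids or immunosuppressives. Oral steroids are prohibited on study (Section 6.7.1, Table 7). Immunosuppressives appear in neither Table 7 nor Table 8. The line is therefore a weak marker, but not an empty one.

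**Step 3. Apply the row to specific cases.**
- Skin changes beyond the local sites that interfere with activity: Grade 2. No difficulty.
- Widespread changes that interfere with activity: Grade 3 by extent. No difficulty.
- Changes that are not widespread but prevent daily activity: extent gives Grade 2. The functional lines cannot raise it, because neither grade goes further than interference. Unless the participant receives a Grade 3 treatment, the result is Grade 2 and no AESI flag. The same degree of disability from pain or bruising would meet the Grade 3 functional line.

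**Step 4. How many participants.** The documents give no erythema rate by grade, so the number of misgraded events cannot be computed. A rough ceiling needs an assumption: that erythema, itching or urticaria of any grade is no more common than injection-site pain, which Section 2.2.7 calls the most frequent reaction and puts at 1 to 4% of participants. For both arms together:
- N = 152: 0.01 × 152 = 1.5 and 0.04 × 152 = 6.1, so about 2 to 6 participants.
- N = 250: 0.01 × 250 = 2.5 and 0.04 × 250 = 10.0, so about 3 to 10 participants.

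These are reactions of any grade, not reactions at the Grade 2/3 boundary. Section 2.3.1 describes earlier injection site effects as mild and transient, so the number affected would be smaller and could be zero. If the combined rate for this row were higher than assumed, the counts would scale in proportion.

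**The case against.** The strongest reply is that the row still has two ordered discriminators, extent and treatment, and that its weaknesses are shared. The bruising row also separates Grade 2 from Grade 3 by unmeasured size words. The pain row's Grade 3 treatment line also names a restricted class, narcotics, which Table 8 allows only after trauma or surgery. This stands: unquantified extent and a restricted drug in the treatment line are not defects peculiar to erythema. The missing functional step is peculiar to it, and the reply does not address that.

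A reader might infer that erythema cannot reach Grade 3 at all, because oral steroids are prohibited. The documents do not support this. Extent alone can give Grade 3, immunosuppressives are not in the prohibited tables, and Section 10.1.6.6 allows deviations with the Medical Monitor's approval or to remove an immediate hazard.

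A reader might also infer that two severity scales compete. Section 10.2.4 says "The Investigator will make an assessment of intensity for each AE and SAE reported during the study" and defines "Moderate: An event that causes sufficient discomfort and interferes with normal everyday activities" and "Severe: An event that prevents normal everyday activities", so widespread erythema that only interferes would look severe on one scale and moderate on the other. The documents settle this. Section 8.5.4.3 sends the grading of reaction severity to Appendix 3, Section 10.3 sets its own four-level reporting scale, and footnote a of Table 6 says "Injection Site Reactions are a category of AEs and should be recorded as AEs using these grading guidelines". These specific provisions govern, and no change to Section 10.2.4 is needed.

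Several safeguards also limit the consequence:
- Grading is blinded, so misgrading has no evident route to favour an arm.
- A reaction that also causes Grade 3 pain or bruising reaches Grade 3 through those rows.
- Every injection site reaction is to be reported as a TEAE, and unresolved ones are followed until they resolve.
- The Sponsor makes the final AESI decision (Section 8.5.4). That could rescue a flag, but it supplies no grading criterion and does not change the grade in the SAP tables.

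**Conclusion.** The Grade 3 erythema cell is wrong as written. The functional criterion that marks Grade 3 in the other two rows is absent, and the AESI rule depends on that grade. Erythema, itching or urticaria that prevents daily activity without being widespread would be graded 2 and not flagged.

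The point is minor. Its size is unknown and may be zero events; the any-grade counts above rest on a borrowed pain rate and do not measure the defect. SAP 8.5.2 has no separate erythema type, and safety is summarized descriptively without formal tests. The effect is therefore limited to descriptive reaction-grade and AESI counts. No efficacy result, sample size or error rate is involved.

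The conclusion assumes that sites apply the table as written. Table 6 was compiled from two outside grading scales, and whether this cell follows either of them cannot be checked from the documents.

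**What to change.** 1. In Table 6, change the Grade 3 functional line of the erythema/itching/urticaria row to "Precludes daily activity", matching the pain row.
2. Add a note to Appendix 3: for this row, assign the higher grade met by extent or by function; treatment lines are examples, are not required for a grade, and do not lift the restrictions in Section 10.4.

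Erythema that prevents activity then reaches Grade 3 by function. Widespread erythema that only interferes remains Grade 3 by extent. The pain and bruising rows are unchanged. The word for widespread changes stays unquantified, so extent remains a matter of judgement, but it no longer carries the threshold alone.

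The cost is one cell, one note and a memo to sites. No new data are collected. Erythema events already graded 2 or 3 need a blinded check against the new wording.

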**10.4. Appendix 4. Prohibited Medications and Procedures****Table 7 Prohibited Medications – Steroids**

Drug	Example of Common Name(s)	Maximum Dose Allowed During Study
Steroids		
Injected or oral corticosteroids a	prednisone, betamethasone, dexamethasone, cortisone, hydrocortisone, triamcinolone	None
Topical corticosteroids on the lower legs or feet	prednisone, betamethasone, dexamethasone, cortisone, hydrocortisone, triamcinolone	None on the lower legs or feet b

a Inhaled, ocular, and intra-articular steroids are allowed.

b Topical corticosteroid use is allowed on body surfaces other than the lower legs and feet.

**Table 8 Prohibited Medications and Procedures – Opioids and Other Therapies**

Drug or Procedure	Maximum Dose Allowed During Study
Acupuncture	None
Anesthetic creams (for use only during injections) and patches, including capsaicin, on lower legs and feet	None
Benzodiazepines	None, except for stable bedtime dose
Gabapentin, pregabalin	None
Isosorbide dinitrate spray on lower legs and feet	None
Opioids (e.g., morphine, oxycodone, tramadol, methadone, fentanyl)	None, except after trauma or surgery
Skeletal muscle relaxants (e.g., cyclobenzaprine, metaxalone, chlorzoxazone)	None
Transcutaneous electrical nerve stimulation	None

## 10.5. Appendix 5. Abbreviations and Definitions

### 10.5.1. Abbreviations

Abbreviation	Definition
ADPS	Average Daily Pain Score
AE	adverse event
AESI	adverse event of special interest
ALS	amyotrophic lateral sclerosis
ALT	alanine transaminase (SGPT)
Anti-HCV Ab	hepatitis C antibodies
APR	Accurate Pain Reporting
AST	aspartate transaminase (SGOT)
β-HCG	Beta human chorionic gonadotropin
BMI	body mass index
BP	blood pressure
BPI-DPN	Brief Pain Inventory for Diabetic Peripheral Neuropathy
BPNS	Brief Peripheral Neuropathy Screening
BUN	blood urea nitrogen
BST	Bedside Sensory Testing
CABG	coronary artery bypass grafting
cDNA	complementary DNA
CDRC	Clinical Data Review Committee
CFR	Code of Federal Regulations
CKD-EPI	chronic kidney disease epidemiology collaboration
CLI	critical limb ischemia
CONSORT	Consolidated Standards of Reporting Trials
CRF	case report form
CRO	clinical research organization
CS	clinically significant
CT	Computed Tomography
DIP	distal interphalangeal
DKA	diabetic ketoacidosis
DM	diabetes mellitus
DMC	Data Monitoring Committee

Abbreviation	Definition
DNA	deoxyribonucleic acid
DPN	diabetic peripheral neuropathy
DSMB	Data Safety Monitoring Board
ECG	Electrocardiogram
eCRF	electronic case report form
EDC	electronic data capture system
eDiary	electronic diary
eGFR	estimated glomerular filtration rate
EQ-5D	EuroQol Health Utilities Index
FIT	Fecal Immunochemical Test
FDA	Food and Drug Administration
GCP	Good Clinical Practice
GGT	Gamma-glutamyl transpeptidase
GLP	Good Laboratory Practice
HADS	Hospital Anxiety and Depression Scale
HbA1c	Hemoglobin A1c
HBV	hepatitis B virus
HBcAb	hepatitis B core antibody (IgG and IgM)
HBsAb	antibody to hepatitis B surface antigen
HBsAg	hepatitis B surface antigen
HCMV	human cytomegalovirus
HCV	hepatitis C virus
HDL-C	high-density lipoprotein cholesterol
HEENT	head, eyes, ears, nose, and throat
Hgb	Hemoglobin
HGF	hepatocyte growth factor
HIPAA	Health Insurance Portability and Accountability Act
HIV	human immunodeficiency virus
HPV	primary human papillomavirus
HTLV	human T cell lymphotropic virus
IB	Investigator's Brochure
IBC	Institutional Biosafety Committee
ICF	informed consent form

Abbreviation	Definition
ICH	International Council for Harmonisation of Technical Requirements for Pharmaceuticals for Human Use
IFN- $\gamma$	interferon gamma
IgG	immunoglobulin G
IgM	immunoglobulin M
IHD	ischemic heart disease
IL-1 $\beta$	interleukin-1beta
IM	Intramuscular
IND	Investigational New Drug application
IRB	Institutional Review Board
ISDN	isosorbide dinitrate
ISR	injection site reaction
ITT	intent-to-treat
IUD	intrauterine device
IWRS	Interactive Web Response System
LDL-C	low-density lipoprotein cholesterol
mITT	modified intent-to-treat
MNSI	Michigan Neuropathy Screening Instrument
NCS	not clinically significant
NDA	New Drug Application
NHU	nonhealing foot ulcer
NIH	National Institutes of Health
NRS	Numerical Rating Scale
OSP	Office of Science Policy
P-A	posterior to anterior
Pap	Papanicolaou
PAD	peripheral arterial disease
PCR	polymerase chain reaction
PCP	Phencyclidine
PDR	proliferative diabetic retinopathy
PE	physical examination
PGIC	Patient Global Impression of Change
PHI	protected health information
PI	Principal Investigator

Abbreviation	Definition
PKC	Protein kinase C
PP	per protocol
PRO	Pro re nata (“as the situation demands”)
PRR	Placebo Response Reduction
PSA	Prostate Specific Antigen
QC	quality control
QoL	Quality of Life
ROS	reactive oxygen species
SAE	serious adverse event
SAP	statistical analysis plan
SF-36	36-Item Short Form Health Survey
SoA	Schedule of Activities
SOP	standard operating procedure
SSRI	selective serotonin reuptake inhibitor
SUSAR	suspected unexpected serious adverse reaction
TCA	tricyclic antidepressants
TEAE	treatment-emergent adverse event
TESAE	treatment-emergent serious adverse event
TENS	transcutaneous electrical nerve stimulation
THC	Cannabinoid
TNF- $\alpha$	tumor necrosis factor alpha
VAS	Visual Analog Scale
VEGF	vascular endothelial growth factor
WFI	water for injection

[figure not shown]

[figure not shown]
**10.5.2. Definitions**

Active Infection	Chronic infection or severe active infection that may compromise the Participant's well-being or participation in the study, in the Investigator's judgment
Allowed Opioid Use	When Participants require opioids for non-DPN post-trauma pain or pain after surgery that was unanticipated during Screening, short-acting formulations are to be used, enabling a more rapid washout and reduced effect on DPN-related pain
Average Daily Pain Score (ADPS)	The mean of at least 5 daily pain scores recorded for Question 5 of the BPI-DPN (Section 10.7) in eDiary during the 7 days prior to the Visits on Day 0, Day 90, and Day 180
Worst Daily Pain Score	The mean of at least 5 worst daily pain scores recorded for Question 3 of the BPI-DPN (Section 10.7) in eDiary during the 7 days prior to the Visits on Day 0, Day 90, and Day 180
Day 14, etc.	Day 14 (for example) refers specifically to the actual day of the Visit designated as the Day 14 Visit, and not to the 14 th day of the study for a Participant.
Drug Abuse	The habitual taking of addictive or illegal drugs
Drugs of Abuse	Amphetamines, barbiturates, benzodiazepines, buprenorphine, cocaine, fentanyl, meperidine, methadone, opiates, oxycodone, oxymorphone, phencyclidine, tramadol
EMLA Cream	A mixture of lidocaine 2.5% and prilocaine 2.5%
First-degree relative	Parent, sibling, or child
Highly Effective Contraception Method	See Section 8.5.7
Injection Site Reaction	An AE located in close proximity to the injection sites on the calves and first observed within 48 hours following Study Injections
Investigator	The PI or appropriate Study Site personnel whom the PI designates to perform a certain duty
Lower Leg	The part of the leg between the knee joint and the ankle joint. Does not include the foot.
Medical Monitor	The Responsible Medical Officer or designee
Participant	An individual who has signed informed consent to be entered into the study
Placebo	Placebo comprises 45 mg sodium chloride and 55 mg sucrose in 5 mL of water for injection. Engensis vials contain the same excipients.
Primary HPV Test	A Primary HPV test is an HPV test that is done by itself for screening. The US Food and Drug Administration has approved certain tests to be primary HPV tests. This is the recommended test by the ACS; however, it is not always available.

Safety Analysis Population	All Participants who receive a Study Injection
Site	A clinical research facility participating in the VMDN-003-2 study
Sponsor	Helixmith Co., Ltd. and its representatives contracted to provide services for study conduct
Stable Dosing Regimen	$\leq 50\%$ change in total daily dose relative to dosing at baseline of any medication
Stage 4 or 5 Kidney Disease	eGFR $< 30$ mL/min/1.73 m 
Study Drug	Engensis or Placebo
Study Injection	Injection of Engensis or Placebo
Treatment Cycle	Two sets of Study Injections 14 days apart comprising a single dose
Unstable Diabetes	Elevations and/or depressions in blood sugar causing episodes of diabetic ketoacidosis (DKA) and/or hypoglycemia

[figure not shown]
10.6

[figure not shown]

[figure not shown]

